This research will enroll 225 adult smokers in a mixed design study with a withinsubjects factor (active nicotine patch vs. placebo patch) and a between-subjects factor (alternative products; VLNCs, Juul e-cigs, or no product). Participants will be randomized to receive either 4 weeks of VLNCs, 4 weeks of Juul e-cigs, or no alternative product. After one week practicing with the alternative product, participants will complete the first of two 7-day switching trials during which they will be asked to refrain from smoking their own cigarettes and encouraged to use the alternative product to which they have been assigned (although the no alternative product group will not have any other products to use). See Figure 3. All participants will be given 8 patches (active nicotine or placebo, in counterbalanced order, with one extra in case of mishaps) to use during the Switch Week. After this first Switch Week, they will smoke normally for one week and then have their second Switch Week using the other type of patch (active or placebo; see Figure 3). We opted to use a 7-day switching phase and only repeat it once to minimize the attrition that was problematic in other studies with longer experimental phases (e.g., three 10-day switching phases produced 45% attrition in the non-step down VLNC group¹¹²). Participants will complete ecological momentary assessments (EMAs) on smartphones at prior to and during the 4 weeks of product use. EMA targets include own cigarette use, alternative product use, withdrawal symptoms, rewarding value of product use (e.g., taste, buzz), and environmental and affective context of any tobacco product use. We will then conduct a 3-month follow-up to assess own cigarette and e-cig use, risk perceptions, and future use intentions. This design addresses the six critical methodological issues for understanding the impact of alternative products outlined by Villanti et al.¹¹³: 1) rigorously assesses the key outcome (conventional cigarettes smoked); 2) assesses product use during switching; 3) uses appropriate control/comparison groups; 4) measures product exposure/use that precedes switching; 5) evaluates the dose and duration of the product exposure/use; and 6) has clear evaluation of the type and quality of the products used (e.g., satisfaction).

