Eligibility criteria include: 1) \geq 21 years old; 2) able to read and write English; 3) no plans to quit smoking in the next 30 days; 4) not currently taking smoking cessation medication; 5) willing and medically able to use nicotine patches, very low nicotine cigarettes, and e-cigarettes; 6) not currently in treatment for psychosis or bipolar disorder; 7) smoking \geq 5 cigarettes per day for the past 6 months; 8) exhaled carbon monoxide (CO) > 5 ppm; 9) no e-cig use within the last month; and 10) not currently pregnant or breastfeeding. We chose to exclude recent e-cig users to minimize the likelihood that participants would chose to use their own e-cig vs. the study ecig. We opted not to exclude ever e-cig users to enhance the external validity of these findings. Analyses will examine the influence of prior e-cig use. It should be noted that use of other tobacco products (e.g., cigars, chew, snus) will not be exclusionary to enhance the external validity of the findings, but we will track such use. Incarcerated individuals will not be enrolled in this study. If study staff members learn that a participant is incarcerated at a time point subsequent to enrollment, the participant will be withdrawn.

Study Visits and Phone Contacts

Interested smokers will complete a phone screen to determine initial eligibility. Potentially eligible smokers will attend an Orientation visit where they will receive a detailed description of the study and provide written informed consent. Participants will then provide a breath sample to verify eligibility (CO > 5 ppm). Eligible participants will also be trained to use the smartphone to complete daily assessments, using the training that was effective in our prior research, and will schedule future study visits (see Table 1). At Visit 1, participants will be randomized to receive VLNCs, e-cigs, or no alternative product and will be trained to use the

"Understanding the real-world impact of the use of three alternate nicotine-delivery products on combustible cigarette use" PI: [name]; UW-CTRI Grant: R01CA239309

	Orientation	V1	V2	V3	V4	V5	V6	V7	Call
Day	0	1	8	11	15	22	25	28	
Week	0	1	2	2	3	4	4	5	3 mo
Consent	Х								
Demographics	Х								
Tobacco use history	Х								
Dependence	Х								
Psychiatric history	Х								
Risks perceptions	Х							Х	Х
Future use intentions	Х							Х	Х
Switching Weeks			Switch Week 1			Switch Week 2			
Alternate product use		Х	Х	Х	Х	Х	Х	Х	Х
Smoking	Х	Х	Х	Х	Х	Х	Х	Х	Х

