Cigarette and product evaluation	Х	Х	Х		Х	Х		Х	
Carbon Monoxide	Х	Х	Х	Х	Х	Х	Х	Х	
Cotinine		Х	Х	Х	Х	Х	Х	Х	
Ecological momentary assessments	Х	Х	Х	Х	Х	Х	Х	Х	
Adverse health events			Х	Х	Х	Х	Х	Х	

Table 1. Study Assessments

product [if applicable]. The study database will randomize participants, stratified by clinic, gender, and race [White vs. Non-White], to enhance scientific rigor and reproducibility. Participants will use their alternative products as they would like for one week to become comfortable with the product¹¹⁴. Participants will also provide a urine sample for cotinine assessment and be given eight study patches to use during Switch Week 1 when all participants will be asked to abstain from using their own cigarettes for the week. At Visit 2, all participants will complete assessments, provide a breath sample for CO assessment and a urine sample for cotinine assessment, receive feedback on their compliance with the smartphone assessments. All participants will then attend a mid-Switch Week visit (Visit 3) and an end-of-Switch Week visit (Visit 4) to assess biomarkers (a breath sample for CO assessment and a urine sample for cotinine). At Visit 4, the end of Switch Week 1, all participants will be told that they can smoke as usual for a week. In addition, all participants will be given the other type of patch (active or placebo) and asked to use these patches at the start of Switch Week 2 (Visit 5) when they are asked to abstain from smoking their own cigarettes for a week. As during the prior Switch Week, all participants will attend visits mid-week and at the end of the week to assess biomarkers (Visits 6 and 7). To enhance reproducibility, we will attempt to schedule appointments at the same time of day (i.e., within a 2-hour window) for each participant so that there is consistent time for product use prior to providing the biological samples across study visits. We opted to use a 7-day switching period to provide a stronger test of the ability of these alternative products to substitute for cigarettes than in our prior study⁵⁰ (A.5.1), but to minimize the retention problems seen in studies with longer switches¹¹². There are also strong theoretical and empirical reasons to suspect that withdrawal and other motivations for cigarette use will be strongest in the first 7 days of switching, and this design will allow sampling of the full range of work/nonwork environments for most participants¹¹⁵. Participants will complete a follow-up assessment call at 3 months. The baseline visit will last 2 hours, but subsequent visits will last <30 minutes.

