The primary aim of this research is to examine the ability of VLNCs and e-cigs to substitute for smokers' usual cigarettes compared to each other and to no alternative product use (Product between-subjects effects) and whether these effects are influenced by steadystate nicotine (Patch within-subjects factor; active vs. placebo patch). The primary analysis model will consist of a mixed analysis of variance (ANOVA) with three levels of the Product between-subjects factor (VLNCs, e-cigs, no alternative product) and two levels of the Patch within-subjects factor (active nicotine patch, placebo patch). To address the primary aim, we will explore statistically significant main or interaction effects in the mixed ANOVA by means of unadjusted simple main effects, interaction contrasts, and pairwise comparisons^{156,157}. Specifically, we will examine the main effect of Product to evaluate the hypothesis that participants who do not have an alternative product will report smoking significantly more of their own cigarettes during the Switch Weeks compared to those who have VLNCs or e-cigs. We will also conduct a pairwise comparison to explore whether there is a significant difference in the number of conventional cigarettes smoked in the VLNC vs. e-cig conditions. We will use the main effect of Patch (active vs. placebo) to evaluate the hypothesis that participants will report smoking fewer of their own cigarettes during Switch Weeks when they receive active nicotine patches compared to placebo patches. We will also test the Patch x Product interaction, with follow-up pairwise comparisons, to examine whether steady-state nicotine produces a differential effect on the number of conventional cigarettes smoked, based on which alternative product a participant was assigned to receive.

The primary outcome is the number of conventional cigarettes smoked during each Switch Week. Based on the literature and our own research, it is possible this outcome will not be normally distributed (i.e., a substantive proportion of participants may smoke no conventional cigarettes during a Switch Week). Therefore, prior to conducting main analyses, we will examine the distributional characteristics of the primary outcome to determine if a transformation is needed (e.g., if the distribution substantially deviates from a normal distribution).

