Finally, there is a small risk of loss of confidentiality. This could occur through a number of possible avenues, all highly unlikely due to the data security measures in place. The University of Wisconsin's Center for Tobacco Resesarch and Intervention (UW-CTRI) computer system is linked to the UW network through a firewall, which is managed by the School of Medicine and Public Health network team, via a fiber link which is maintained by the UW Division of Information Technology. No data are stored on individual computer hard drives. All data are transmitted from the point of collection to the UW-CTRI server through secure, encrypted web connection. There are rare occasions when, due to a loss of internet access or computer hardware failure, data are collected in paper forms, which could be taken or lost. In addition, consent forms are obtained in paper copy; these forms contain the participant name and signature. Finally, the University of Wisconsin and the National Cancer Institute may inspect the signed consent forms. Because of this possible need to release information to these parties, we cannot guarantee absolute confidentiality.

Participants will be informed about all of these risks prior to providing written informed consent.

Adequacy of Protection Against Risks

Recruitment and Informed Consent. Participants will be recruited from the greater Madison and Milwaukee, WI areas via the media recruitment methods (i.e., TV, newspaper, and earned media) that have recruited thousands of smokers. We will also use Internet/Facebook advertisements that have been successful in our recent e-cig studies. Interested potential participants will contact the study via phone. Study staff will call interested potential participants within 48-72 hours to introduce the study, assess interest and screen for eligibility. If the person is interested and eligible, an in-person Orientation Visit will be scheduled. At this visit, the smoker will learn about general requirements for participation (e.g., need to switch from using their own cigarettes for 2 7-day Switch Weeks, participation in assessments) as well as risks associated with nicotine withdrawal, alternate product use, patch use, and the possible loss of confidentiality. Study staff will then provide each study candidate with an IRB-approved

"Understanding the real-world impact of the use of three alternate nicotine-delivery products on combustible cigarette use" PI: [name]; UW-CTRI Grant: R01CA239309

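### Table 1 puts the end of Switch Week 2 six days after its start, against seven for Switch Week 1; this contradicts the table's own week label and the 7-day text, and no counting window is defined for the primary outcome

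*Combined protocol and SAP*

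**What the plan says.** **Table 1 (Study Assessments).** For Orientation and Visits 1 to 7, the Day row reads "Day 0 1 8 11 15 22 25 28". The Week row, which also covers the follow-up call, reads "Week 0 1 2 2 3 4 4 5 3 mo". Visit 7 is therefore on Day 28 and in Week 5.

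**Study Visits and Phone Contacts.** Switch Week 1 runs from Visit 2 to Visit 4, the end-of-week visit. Switch Week 2 starts at Visit 5, with Visit 6 in mid-week and Visit 7 at the end. Each participant's visits are to be held at the same time of day, within a 2-hour window where possible.

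**Length of the Switch Weeks in the text.** The study overview describes "the first of two 7-day switching trials". Recruitment and Informed Consent says candidates will be told of the "need to switch from using their own cigarettes for 2 7-day Switch Weeks". The nicotine patch paragraph supplies seven days of patches plus one spare for each Switch Week. The Analytic Plan refers to seven days of data in the Switch Weeks.

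**Primary outcome (Analytic Plan).** "The primary outcome is the number of conventional cigarettes smoked during each Switch Week". It is a count, not scaled per day, and no day or hour is given at which counting starts or stops. The model is a mixed ANOVA with Product (three levels) and Patch (two levels). It has no period or order term.

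**The concern.** Table 1 is the schedule that staff will use to book visits. As it stands, it gives two visit-to-visit intervals of different length for two periods that the text treats as equal. The primary outcome is a raw total per period, so a difference in observed time would go straight into the count.

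The Patch effect, and its interaction with Product, compare one Switch Week with the other in the same person. A shorter second week would act as a period effect. With no period term, that effect has two places to go. It goes into within-person error when patch order is balanced, and partly into the Patch estimate when order is unbalanced among those analysed. The end-of-week CO and cotinine readings would also follow different lengths of switching.

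**Working it through.** **1. Interval lengths, from the Table 1 Day row**

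| Interval | Switch Week 1 | Switch Week 2 |
|---|---|---|
| Start to end visit | 15 − 8 = 7 days | 28 − 22 = 6 days |
| Start to mid-week visit | 11 − 8 = 3 days | 25 − 22 = 3 days |
| Mid-week to end visit | 15 − 11 = 4 days | 28 − 25 = 3 days |

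The stated seven days is reproduced for Switch Week 1 but not for Switch Week 2, which is 1/7 (14%) shorter.

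**2. Week labels.** In Table 1, Days 1, 8, 15 and 22 open Weeks 1 to 4, so week = floor((day − 1)/7) + 1. This reproduces the printed label for Visits 1 to 6. For Visit 7, floor(27/7) + 1 = 4, but the table prints 5. By the same rule Week 5 opens on Day 29. Day 28, Week 5 and a seven-day visit-to-visit interval cannot all hold.

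**3. Possible shift in the Patch effect.** Let m be own cigarettes per day during a Switch Week. The documents give no value for m, so 1, 3 and 5 are assumptions. Suppose the second period loses one day. Let n1 participants in an arm have active patch first and n2 have it second. The active-minus-placebo difference moves by +m for the first group and −m for the second, so

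shift = m × (n1 − n2)/(n1 + n2).

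The power section gives 54 analysed per group. With 27:27 the shift is 0. With 30:24 (an assumed split):

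- m = 1: 1 × 6/54 = 0.11 cigarettes per week
- m = 3: 3 × 6/54 = 0.33
- m = 5: 5 × 6/54 = 0.56

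How likely is such a split? Assume 225/3 = 75 per arm, order 37:38, and random loss to 54 (hypergeometric). A split of 30:24 or more uneven, in either direction, has probability 0.21 in a given arm. For at least one of three arms it is 1 − (1 − 0.2055)³ = 0.50.

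**4. Possible loss of precision under balanced order.** The power section gives SD 6 and correlation 0.5, so the SD of the paired difference is 6 × √(2 × (1 − 0.5)) = 6. A period shift of ±m in equal halves raises it to √(36 + m²). The table shows power for the plan's within-subject difference of 2.8 at n = 54, two-sided 5% paired t-test. The significance level is assumed, since the plan does not state it.

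| m | SD of difference | Power for 2.8 |
|---|---|---|
| 0 | 6.00 | 0.920 |
| 1 | 6.08 | 0.913 |
| 3 | 6.71 | 0.853 |
| 5 | 7.81 | 0.735 |

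This reads the plan's SD and differences as cigarettes per week (the power section does not give the unit) and takes m as the same for everyone.

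**The case against.** The strongest reply is that the conflict is clerical and that the counts need not be unequal. A reader might infer from Table 1 that every participant's second count is one day short, and that the Patch effect is therefore biased. The documents do not support either inference.

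- No section says the count runs from visit to visit. Use is recorded by day, through a button press at each cigarette and an evening report, with timeline follow-back of daily use as the supplement.
- In calendar days, Days 8 to 14 and Days 22 to 28 are both seven days. Day 28 also closes the four weeks of product use, through which smartphone assessment continues.
- Every statement in the text gives seven days, and the table's own Week 5 label disagrees with Day 28. A slip in one cell is at least as plausible as a planned six-day week.
- Even with a short week, each completer has one period of each length, so Product comparisons rest on equal total exposure. Patch order is counterbalanced, so the expected shift in the Patch effect is zero. The shifts shown are for one arm, and the Patch main effect pools three.
- Participants are asked to abstain in Switch Weeks, and the Analytic Plan expects that many may smoke none of their own cigarettes, so m may be small.

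Most of this stands, and it limits the point to a conditional one. It does not remove the contradiction. The inclusive-day reading also leaves a gap: with visits at a fixed time of day, Visit 4 on Day 15 follows seven complete days (Days 8 to 14), whereas Visit 7 on Day 28 follows six (Days 22 to 27) and part of a seventh. Visit 7 is the last visit, so no later visit can fill in the rest of Day 28 by timeline follow-back.

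**Conclusion.** Wrong as written, of minor severity. Two things are established. The Visit 7 entries in Table 1 contradict each other and the seven-day text. The primary outcome also has no stated start and stop for its count.

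An unequal window is a risk, not a fact. It needs Visit 7 to be held on Day 28 and the count to stop at that visit. If both happen, the second-period count covers about one day less. Product comparisons keep equal total exposure, and balanced order leaves no expected Patch bias. What remains is extra within-person error, and a chance shift in an arm's Patch effect of about 0.1 to 0.6 cigarettes per week for a 30:24 split at m = 1 to 5. Both the split and the values of m are assumptions; the precision figures further assume that the plan's power inputs are weekly.

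**What to change.** Reconcile the Day and Week entries for Visit 7 in Table 1 with the seven-day text, so that both Switch Weeks have the same length.

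Add one sentence to the Analytic Plan defining the counting window: own cigarettes over the same seven complete days in each Switch Week, with the first and last day named, or own cigarettes per observed day. Either removes the dependence on visit timing. The per-day form matches the plan's own summary measure of alternative product use, which is already a daily mean.

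The cost is a correction to the Visit 7 column of one table and one sentence of text. No new assessments are needed, and the sample size does not change.

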Visit assessments. At each study visit, participants will complete assessments of affect using the well-validated Positive and Negative Affect Scale (PANAS¹²⁷), withdrawal symptoms using the validated Wisconsin Smoking Withdrawal Scale (WSWS¹²⁸), and craving using the Brief Questionnaire of Smoking Urges (QSU-Brief^{129,130}) from the PhenX Toolkit. At Visits 1 through 7 participants will complete the modified Cigarette Evaluation Scale (mCES^{71,131,132}) for cigarettes and at Visits 2 through 7 they will complete the mCES for their assigned alternative product based on their reactions in the last 24 hours. The 12 items of the mCES assess product satisfaction, psychological reward, aversion, enjoyment of respiratory tract sensations, and craving reduction. We will use timeline follow-back methods^{133,134} to assess daily use of participants' own cigarettes, assigned alternative products, and patch if the visit occurs during a Switch Week. These data will be used to supplement EMA reports in case of missing EMA data. Participants will also be asked at all visits except Visit 1 (when they will not have any study products or medication yet) about any possible adverse events from using VLNCs, e-cigs or the patches¹³⁵. At the final visit (Visit 7), we will again assess acceptability, risk perceptions, and

"Understanding the real-world impact of the use of three alternate nicotine-delivery products on combustible cigarette use" PI: [name]; UW-CTRI Grant: R01CA239309

intentions to use cigarettes, VLNCs, e-cigs, and patches. We will also assess how the Juul e-cig compares to other e-cigs participants have used, including what they like or do not like Juul, using a combination of questionnaires and open-ended questions to provide additional information regarding Juul acceptability among adults.

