own cigarette), there is approximately a 30% chance a more comprehensive assessment (3) minutes) will be triggered that will include: 1) time since prior use of cigarette/alternative product), 2) use context (e.g., smoking prohibited, others vaping/smoking, home, work), activity, and withdrawal symptoms and affect prior to use, and 3) individual items from the mCES that tap potential mechanisms (e.g., product satisfaction, psychological reward, aversion, enjoyment of respiratory tract sensations, and craving reduction). The comprehensive assessments will be specific for each type of use event (i.e., cigarettes, VLNCs, and e-cigs). All participants will complete an evening assessment prior to going to bed. Evening reports (5 minutes) will assess: affect, withdrawal, use of cigarettes and alternative products, overall satisfaction with cigarettes/alternative products, use of patch during Switch Weeks, smoking cues, stressors, and pleasure in daily activities. Participants will spend less than 25 minutes each day recording use events and answering questions, eliminating the problems of recall bias or participants prefilling or back-filling a traditional daily diary. This approach is more rigorous than relying on participants to document their use of non-experimental products using a paper and pencil log¹⁴². We have conducted numerous EMA studies and will use the strategies that have been successful in our earlier work: training in assessments, ability to briefly postpone assessments, use of counters, etc.^{50,86,143}. This frequency of assessment is of moderate intensity relative to protocols used in our prior work⁸⁶.

Follow-up assessment call. Three months after Visit 1, participants will complete a brief follow-up assessment call to assess current smoking, use of any alternative products, motivation and self-efficacy for smoking cessation, risk perceptions, and future plans to use VLNCs, e-cigs, and patches.

Participants who are interested in quitting smoking after Visit 7 will be offered the Wisconsin Tobacco Quit Line toll-free number? ([name]) and the phone number(s) for smoking cessation studies being conducted at our Center.

Alternative Products and the Nicotine Patch

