The secondary outcome is number of VLNCs or JUUL pods used during each switch week. This research will also examine the main effects for Product and Patch and the Product X Patch interaction effect on other exploratory outcomes: 1) the proportion of conventional cigarettes replaced; 2) the use of alternative tobacco products; 3) use contexts; and 4) potential mechanisms such as rewarding value of the alternative products and conventional cigarettes, alleviation of withdrawal symptoms, and taste. We will also explore the impact of person factors (e.g., sex, education, psychiatric comorbidity, dependence) and risk perceptions on the primary, secondary, and exploratory outcomes. We will include these variables as covariates in the analyses, and we will include covariate interaction terms with the between- and within-subjects factors (e.g., sex x Product; sex x Product x Patch) to determine whether these individual difference variables moderate the ability of the alternative products to substitute for conventional cigarettes. To examine use contexts and putative mechanisms driving alternative product use and substitution for conventional cigarettes, we will use the daily EMA data from the evening reports as well as data from the quasi-random daily assessments that will be collected during the Switch Weeks as described above as the exploratory outcome variables. One set of analyses will test summary versions of the outcomes (e.g., means or counts across the Switch Weeks); another set of more fine-grained analyses will preserve the intensive longitudinal data (ILD) aspect of the EMA data collected during each of the 7 days of the Switch Weeks. For the summary versions of the outcomes, the alternative product use outcome will consist of the mean alternative product use events per day reported during the Switch Weeks and the context

"Understanding the real-world impact of the use of three alternate nicotine-delivery products on combustible cigarette use" PI: [name]; UW-CTRI Grant: R01CA239309

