and mechanisms variables will be based on means across the 7 days of the Switch Weeks. For these summary outcomes, we will use statistical models similar to the analyses described above for the primary outcome. For the ILD outcomes, we will create one set of outcomes based on the evening report that assesses experiences across the full day and another set based on the 3 quasi-random comprehensive assessments that occur during the day. For the ILD versions of the outcomes, we will use conditional growth curve models that permit slope and intercept parameters to be evaluated across the 7 days of the Switch Weeks as a function of group; these models also permit examination of other forms of change over time (e.g., linear, quadratic, cubic). We will explore two main approaches to growth curve modeling: a multilevel modeling (MLM) approach¹⁵⁸ and a structural equation modeling (SEM) approach¹⁵⁹. Although similar, each of these modeling approaches has advantages and disadvantages¹⁶⁰ that we will exploit in exploratory analyses. While we are not powered to detect mediation due to funding limitations, we will conduct exploratory mediation analyses to provide information for future research on whether these mechanisms mediate the effects of alternative product use on the use of conventional cigarettes.

Power for Primary Aim Hypotheses

With attrition-adjusted n=54 per group for a between-subjects pairwise comparison, the study is powered to detect a difference of 3.3 cigarettes (SD=6); a corresponding within-subjects pairwise comparison (SD=6, correlation=0.5) is powered to detect a difference of 2.8 cigarettes. Thus, we feel that a total N=225 provides adequate power to detect predicted effects.

Protection of Human Subjects

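### Event-triggered EMA ratings of cigarette reward come only from participants who smoke in a Switch Week, so the planned Product test on these items can show a difference without any effect on reward

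*Combined protocol and SAP*

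**What the plan says.** The secondary aims name mechanisms of product use, such as taste and satisfaction. In the Analytic Plan these become exploratory outcomes, the last of which is "4) potential mechanisms such as rewarding value of the alternative products and conventional cigarettes", each tested for Product, Patch and their interaction. On the data source the plan says: "we will use the daily EMA data from the evening reports as well as data from the quasi-random daily assessments". In the summary form, the context "and mechanisms variables will be based on means across the 7 days of the Switch Weeks", and the model is to resemble the one for the primary outcome.

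The cigarette-reward data come from three places:

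- **Event-triggered EMA** (Assessments, Ecological momentary assessments). After each press of a use button "there is approximately a 30% chance a more comprehensive assessment" will follow. It carries individual items from the modified Cigarette Evaluation Scale (mCES) and is specific to the product just used.
- **Evening report** (same section). "All participants will complete an evening assessment prior to going to bed", and its content includes overall satisfaction with cigarettes.
- **Visit mCES** (Visit assessments). The cigarette form is scheduled at Visits 1 to 7. From Visit 2, participants also "complete the mCES for their assigned alternative product based on their reactions in the last 24 hours". Table 1 marks product evaluation at Visits 1, 2, 4, 5 and 7.

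On the primary outcome, the Analytic Plan says it is possible that "a substantive proportion of participants may smoke no conventional cigarettes during a Switch Week". It hypothesises more own-cigarette smoking without an alternative product than with one, and less on active than on placebo patch. It gives no analysis set, scoring rule or missing-data rule for the reward outcome. Timeline follow-back supplements missing EMA data on product and patch use, not ratings.

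**The concern.** A participant who switches completely, as the trial asks, generates no cigarette event and so no event-triggered cigarette rating. Having a rating is therefore a post-randomisation event that the trial's own hypotheses tie to Product and Patch. If people who find cigarettes more rewarding are also the ones who keep smoking, the arm with the most successful switchers is left with high-reward raters. A product with no effect on cigarette reward could then appear to raise it, or a true reduction could be masked. Ratings of the alternative product have the same structure, since only users supply them.

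At stake is the reading of a mechanism named in the secondary aims. The exploratory mediation analyses, meant to inform later research, would inherit the problem.

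**Working it through.** **Plan's own figure.** The documents give no figure for this outcome. The only relevant anchor is the group size in the power section: 54 per group after attrition, from 225/3 = 75, so 54/75 = 72% retained. That section's between-subjects figure reproduces if two-sided alpha 0.05 and 80% power are assumed (neither is stated): (1.96 + 0.84) x 6 x sqrt(2/54) = 3.24, against the stated 3.3 cigarettes. I use 54 per arm below.

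**Step 1: who has no event-triggered rating.** With about a 30% trigger chance per press, a participant who records k own cigarettes in a week has no rating with probability 0.7^k:

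| k | 0 | 1 | 2 | 3 | 5 | 7 |
|---|---|---|---|---|---|---|
| No rating | 100% | 70% | 49% | 34% | 17% | 8% |

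Non-raters are thus mostly people who smoked nothing or very little. The Analytic Plan also speaks of three quasi-random assessments a day, which does not match a simple 30% rule. Under either scheme, zero cigarettes gives no cigarette rating.

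**Step 2: size of the selection shift.** Let reward have SD 1 and no treatment effect. Let rho be its correlation with the propensity to keep smoking, and p the share who rate. Then mean reward among raters = rho x phi(t)/p, where phi is the standard normal density and t the cut-off that leaves share p. At rho = 0.5:

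- p = 90%: 0.5 x 0.1755/0.90 = 0.10 SD
- p = 70%: 0.5 x 0.3477/0.70 = 0.25 SD
- p = 50%: 0.5 x 0.3989/0.50 = 0.40 SD

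The spurious gap between two arms is the difference of these means:

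| Raters, no product vs product | rho 0.3 | rho 0.5 |
|---|---|---|
| 90% vs 50% | 0.18 SD | 0.30 SD |
| 80% vs 50% | 0.13 SD | 0.22 SD |
| 80% vs 30% | 0.24 SD | 0.41 SD |

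**Step 3: false positives for Product.** Simulation with 3,000 runs per setting, 54 per arm and no true effect on reward. The test is a one-way F across the three arms among people rated in both weeks, who are the complete cases of a mixed ANOVA. Patch does not change who smokes.

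| Still smoking: none / VLNC / e-cig | rho 0 | rho 0.3 | rho 0.5 | Mean rated in both weeks, per arm |
|---|---|---|---|---|
| 95 / 85 / 75% | 5% | 8% | 14% | about 42 |
| 90 / 70 / 50% | 5% | 11% | 24% | about 32 |
| 95 / 60 / 40% | 5% | 16% | 43% | about 29 |

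The e-cig minus no-product gap runs from 0.11 SD (first row, rho 0.3) to 0.47 SD (last row, rho 0.5). It slightly exceeds the Step 2 formula because ratings are required in both weeks. With equal shares in all arms the rate stays near 5%. A separate two-arm t-test simulation gave 9% to 16% at 80% vs 50%, and 13% to 30% at 80% vs 30%, for rho 0.3 to 0.5.

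**Step 4: false positives for Patch.** Paired t-test among people rated in both weeks:

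- Patch does not change who smokes: about 5%.
- Active patch lowers the smoking share by 10 points: 5.5% to 8% (rho 0.3 to 0.5).
- Active patch lowers it by 20 points: 12% to 14% (rho 0.5).

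**The case against.** A reader might go further than the documents allow in four ways.

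- **That no cigarette-reward measure exists for abstainers.** The evening report is completed by everyone and asks about satisfaction with cigarettes, and the cigarette mCES is scheduled at visits for all. The 24-hour window is written beside the alternative-product form and may not govern the cigarette form. These sources are affected only if abstainers skip them or cannot rate, and the plan is silent on that.
- **That the plan forecasts different abstinence rates by arm.** It says zero smoking may occur, and its hypotheses concern cigarette counts. Unequal rating shares are a reasonable inference, not a stated expectation.
- **That Patch is as exposed as Product.** Patch is within-person, so stable differences between people cancel. Bias needs reward in a given week to drive smoking in that week.
- **That a Visit 2 comparison could replace the Switch Week analysis.** Visit 2 comes before the patch and before the request to stop smoking, so it answers a different question.

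It is also fair to say that the size rests on assumptions. Large rating gaps need near-complete abstinence for a week in people enrolled with no plan to quit. The outcome is exploratory, mediation is declared unpowered, and reward from a product is naturally conditional on using it.

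All of this narrows the point but does not remove it. The event-triggered items are still averaged and tested across randomised arms as though everyone could supply them, with no rule for those who cannot.

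**Conclusion.** The point holds for the event-triggered ratings of conventional cigarettes and, by the same reasoning, for product ratings among product users. The between-Product test on these items is conditional on behaviour after randomisation and can be significant when reward is unchanged. The product may cause the selection without changing reward.

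The rates of about 8% to 24% for mild to moderate scenarios (up to 43% in the most extreme one run), against 5%, depend on assumed rating shares and a reward-smoking correlation of 0.3 to 0.5. The documents supply neither. The direction of the bias follows from a positive correlation, and the bias disappears at zero correlation or with equal shares. For the evening and visit items the defect is an unstated scoring rule, not a demonstrated bias. The primary analysis is untouched.

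**What to change.** Amend the mechanism paragraphs of the Analytic Plan in three ways.

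1. Label event-triggered Switch Week ratings of cigarettes and products as conditional on use. Report the number of raters in each Product x Patch cell. Draw no causal Product or Patch conclusion about mechanism from them without a sensitivity analysis that gives non-raters a range of values, or bounds.
2. Add, not substitute, a between-Product comparison of the Visit 2 cigarette mCES adjusted for the Visit 1 mCES. Table 1 marks both. Visit 2 ends the practice week, before anyone is asked to stop smoking, so nearly all participants should be able to rate.
3. State how abstainers' evening-report and visit cigarette items are scored: skipped, answered from recall, or set by rule.

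The cost is wording and slightly more analysis, because the data are already scheduled for collection. The limitation is that the Visit 2 comparison covers the practice week only. It says nothing about reward during switching, Patch or Product x Patch, so those questions stay with the labelled Switch Week ratings and their sensitivity analysis.
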